3.4.3 Additional Secondary Efficacy Endpoints

The endpoints derivation and data handling are described in Section 3.1.4. The numbering of the following endpoints is consistent with Section 2.3.3.

- o CFBL in the 22-item Sino-Nasal Outcome Test (SNOT-22) total score at Week 24 in participants without nasal polyps
- o CFBL in 3CS score at Weeks 4, 8, 12, 16, and 20
- o CFBL in the symptom score for individual cardinal symptoms of nasal blockage/obstruction/congestion, anterior/posterior nasal discharge, and facial pain/pressure at Weeks 4, 8, 12, 16, 20, and 24
- o CFBL in loss of smell score at Weeks 4, 8, 12, 16, 20, and 24, for all participants and for participants with baseline score ≥ 2
- o CFBL in SNOT-22 total score at Weeks 4, 8, 12, 16, and 20
- o CFBL in SNOT-22 subdomain scores at Weeks 4, 8, 12, 16, 20, and 24

The endpoints above will be analyzed similarly to the primary efficacy endpoint but without the sensitivity analysis and supplemental analysis, and the data derivation and handling are described in Section 3.1.4. LS-means of the CFBL in each treatment group and their difference with 95% confidence interval (CI) and p-value will be provided.

- Improvement of ≥ 1 point, ≥ 2 points, and ≥ 3 points from baseline in 3CS score at Week 24
- Improvement of ≥ 8.9 and ≥ 12 from baseline in SNOT-22 total score at Week 24
- Sinonasal surgery requirement through Week 24
- Rescue medicine use through Week 24

- Improvement of ≥ 1 category and ≥ 2 categories in the severity of CRS-related symptoms as indicated by the Patient Global Impression of Severity (PGIS) at Week 24
- Overall change of "very much better" or "much better" in the CRS-related symptom severity as indicated by the Patient Global Impression of Change (PGIC) at Week 24

Participants who receive SCS for any reason and/or are indicated for sinonasal surgery will be considered non-responders for time points after SCS use or surgery. Unless otherwise specified in Section 3.1.4, participants with missing data will be included as non-responders. Comparison between LYR-210 group and the sham procedure group will be performed using logistic regression including nasal polyp status and baseline value. The general association p-value will be provided. The odds ratio and the corresponding CI will also be provided.

- CFBL in the percent opacification of the bilateral anterior and posterior ethmoids at Week 20 as determined by 3-D volumetric CT analysis in participants without nasal polyps
- CFBL in the Zinreich score of the bilateral anterior and posterior ethmoids at Week 20
- CFBL in 36-Item short form health survey, version 2 (SF-36v2) physical health, mental health, and domain scores at Week 24
- CFBL in Medical Outcomes Study Sleep Scale (MOS Sleep-R) score at Week 24

The above endpoints will be analyzed by ANCOVA with fixed-effect terms for treatment group and nasal polyp status, and with baseline score as a covariate. LS-means in each treatment group and their difference with 95% confidence interval (CI) and p-value will be provided.

- Time to first rescue treatment requirement through Week 24

Time to first rescue treatment requirement through Week 24 will be analyzed using the Kaplan-Meier (K-M) method. The K-M estimate of median time to first recommendation of rescue treatment requirement with CI (if estimable) will be presented for each treatment group. Estimates of quartiles (25th and 75th percentiles) will also be presented for each treatment group. Time to first recommendation of rescue treatment will be compared between LYR-210 group and the sham procedure group using the log-rank test stratified by the stratification factor. P-value from the log-rank test will be presented.

- Total SCS dose prescribed through Week 24
- Number of days on SCS through Week 24

The above endpoints will be analyzed by ANCOVA with fixed-effect terms for treatment group and nasal polyp status. LS-means in each treatment group and their difference with 95% confidence interval (CI) and p-value will be provided.

Counts and percentages of subjects taking SCS medications by ATC class and preferred term will be summarized.

- CFBL in EuroQoL 5-dimension, 5-level (EQ-5D-5L) score at Week 24

The EQ-5D-5L descriptive system will be summarized as categorical variables by presenting the frequency and proportion of each level for each dimension by visit and by treatment arm, and analyzed by the Cochran–Mantel–Haenszel (CMH) test controlling for nasal polyp status and baseline score.

The overall health score on a 100-point vertical (visual analogue scale: 0 = worst imaginable health state; 100 = best imaginable health state) will be summarized as continuous variable and analyzed by ANCOVA including fixed-effect terms for treatment group and nasal polyp, and with baseline score as a covariate. LS-means in each treatment group and their difference with 95% confidence interval (CI) and p-value will be provided.

- CFBL in Work Productivity and Activity Impairment-Specific Health Problem (WPAI-SHP), version 2.0 at Weeks 4, 12, and 24

The following will be summarized by visit and analyzed by ANCOVA including fixed-effect terms for treatment group and nasal polyp status, and baseline value as covariate. LS-means in each treatment group and their difference with 95% confidence interval (CI) and p-value will be provided.

- Percent work time missed due to CRS: $Q2/(Q2+Q3) \times 100\%$
- CRS affected productivity: $Q5 \times 10\%$
- CRS affected ability to do regular daily activities, other than work at a job: $Q6 \times 10\%$

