Responder endpoints (eg, improvement of ≥ 8.9 in SNOT-22 and improvement of ≥ 1 point, ≥ 2 points, ≥ 3 points in 3CS) will be analyzed using the CMH test controlling for geographic region and nasal polyp status. Participants who receive SCS for any reason and/or are indicated for sinonasal surgery will be considered nonresponders for time points after SCS use or surgery. Unless otherwise specified, participants with missing data will be included as nonresponders.

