The study treatment will be discontinued and all procedures/assessments for the ET and end of treatment phase (EOTP) visits will be completed prior to the surgery. The participant will be discontinued from the study.

The sinonasal surgery requirement through Week 24 is derived by checking whether the sinonasal surgery is indicated before Week 24, inclusive. If a participant is lost to follow up/discontinues the study before Week 24 and does not have sinonasal surgery requirement at that time, this will be considered as a missing data for the analysis.

3.1.4.10 Total systemic corticosteroid (SCS) dose prescribed through Week 24

SCS for rescue treatment of CRS or for another reason that are prescribed to the participant are to be recorded in the eCRF.

If possible, an endoscopy should be performed before starting treatment with SCS. The participant should continue with the study treatment and follow-up visits per protocol. The investigator (or designee) will record the dates and dosing information (dosage form, daily dose, duration, name of drug) on the appropriate page(s) of the eCRF. Indication for SCS use will also be captured by selecting 1 or more of the following categories:

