5 CHANGES FROM PROTOCOL

There is no change from the protocol-specified statistical analyses.

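### SAP 3.4.3 puts six binary endpoints under one responder rule and one logistic model; the rule conflicts with the derivations of surgery requirement and rescue medicine use, the baseline term does not exist for three endpoints, and the change from the protocol's test is not declared

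*SAP*

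**What the plan says.** SAP 3.4.3 lists six binary endpoints together: 3CS improvement, SNOT-22 improvement, sinonasal surgery requirement, rescue medicine use, PGIS improvement and PGIC response. One paragraph follows for all of them.

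- **Coding:** "Participants who receive SCS for any reason and/or are indicated for sinonasal surgery will be considered non-responders" at time points after the SCS use or surgery.
- **Missing data:** "Unless otherwise specified in Section 3.1.4, participants with missing data will be included as non-responders".
- **Model and p-value:** "logistic regression including nasal polyp status and baseline value. The general association p-value will be provided". An odds ratio with its interval is also to be given.

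Elsewhere:

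- SAP 3.1.4.8 derives rescue medicine use by checking whether rescue medication was taken by Week 24. It has no missing-data rule.
- SAP 3.1.4.9 derives surgery requirement by checking whether surgery was indicated by Week 24. For a participant who leaves early without that event, "this will be considered as a missing data for the analysis".
- Protocol 9.3.2 says that responder endpoints, with SNOT-22 and 3CS improvement as its examples, "will be analyzed using the CMH test controlling for geographic region and nasal polyp status".
- Protocol 9.3.7 requires efficacy analyses to be adjusted for baseline score, region and polyp status unless otherwise noted.
- SAP 5 states: "There is no change from the protocol-specified statistical analyses".

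**The concern.** A responder endpoint and an event endpoint run in opposite directions: *yes* is good for the first and bad for the second. The SAP never says which value a non-responder takes when the endpoint is needing surgery or using rescue medication. Two programmers could follow the paragraph and produce different data. Neither dataset would match the derivations in SAP 3.1.4.

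Three further problems sit in the same paragraph:

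- The model asks for a covariate that PGIC, surgery requirement and rescue use do not have.
- The p-value is named after a CMH statistic, while the comparison is a logistic regression.
- Region, a randomisation stratum under Protocol 3.5.4, is in the protocol's test and missing from the SAP's model, with no change declared.

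At stake is whether the reported surgery and rescue-medication results measure what their names say, and whether the reader knows which test produced the responder p-values.

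**Working it through.** The plan gives no event rates or power for these endpoints, so there is no figure of its own to reproduce. The check is mainly a comparison of texts. The arithmetic below only illustrates size.

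**1. Does the paragraph reach the event endpoints?** Yes. Both are in the list it governs. Within that list, surgery requirement is the endpoint for which SAP 3.1.4 gives a different missing-data rule, so the reference to exceptions there makes sense only if the paragraph covers event endpoints too.

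**2. Coding under each reading of non-responder**

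| | Rescue medicine use | Surgery requirement |
|---|---|---|
| SAP 3.1.4.8 / 3.1.4.9 | medication taken | surgery indicated |
| Non-responder = event *yes* | also counts participants only indicated for surgery | also counts SCS-only users |
| Non-responder = event *no* | SCS users coded as not using it: 0 events | indicated participants coded as not requiring it: 0 events |

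Under the *no* reading both arms have no events (rescue use by SCS, surgery as indicated) and the odds ratio is not estimable.

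**3. Dropouts without an event.** Surgery requirement: left missing (SAP 3.1.4.9). Rescue medicine use: non-responder by the default in SAP 3.4.3, because 3.1.4.8 is silent. Time to first rescue treatment: censored (SAP 3.1.4.7). No reason is given for treating the first two differently.

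**4. Size under the *yes* reading.** Sizes 120 LYR-210 and 60 sham are from SAP 2.2.4; all rates are assumptions. Odds ratio = [a/(120 − a)] / [b/(60 − b)], with a and b the events on LYR-210 and sham.

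*Surgery requirement.* Assume a true rate of 5% in both arms: 6/120 and 3/60, odds ratio (6/114)/(3/57) = 1.00. Add SCS-only users:

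| SCS-only, LYR-210 / sham | Events counted | Odds ratio |
|---|---|---|
| 5% / 10% | 6+6 = 12 vs 3+6 = 9 | (12/108)/(9/51) = 0.63 |
| 10% / 20% | 6+12 = 18 vs 3+12 = 15 | (18/102)/(15/45) = 0.53 |
| 15% / 30% | 6+18 = 24 vs 3+18 = 21 | (24/96)/(21/39) = 0.46 |

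The apparent surgery benefit comes entirely from SCS use.

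*Rescue medicine use.* Assume 10% vs 20%: 12/120 and 12/60, odds ratio (12/108)/(12/48) = 0.44. Count dropouts without an event as users, at the same rate in each arm:

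- 5%: 18 vs 15 events, odds ratio 0.53.
- 10%: 24 vs 18 events, (24/96)/(18/42) = 0.58.

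**5. Does a baseline value exist?** SAP 3.1.3 defines it as the last non-missing value up to the day of treatment.

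- PGIC rates change since before treatment (SAP 3.1.4.17). It is not among the Day 1 questionnaires (Protocol 3.5.3) and is scheduled only at Week 24 (Protocol Table 4).
- Rescue treatment, by SCS or recommended surgery, is defined as occurring after randomisation (Protocol 3.4.3), and needing rescue medication in the run-in bars enrolment (Protocol 3.5.2).

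In a test fit with 12 events per arm, a baseline-rescue column equal to 0 for everyone gave a singular design (4 columns, rank 3). A PGIC baseline missing for everyone left no records. Treatment plus polyp status alone fitted, with odds ratio 0.44.

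**6. Test and covariates**

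| | Protocol 9.3.2 | SAP 3.4.3 |
|---|---|---|
| Method | CMH | logistic regression |
| Region | yes | no |
| Polyp status | yes | yes |
| Baseline value | no | yes |
| p-value | from CMH | labelled *general association*, a CMH statistic |

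At least for the 3CS and SNOT-22 responders, which the protocol names, the method has changed, so the statement in SAP 5 is not accurate.

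**The case against.** The best defence is that the coding is already given. SAP 3.4.3 opens by referring derivation and data handling to SAP 3.1.4, where each event is counted by itself; a programmer who used only 3.1.4 would code both correctly. The rule also carries a time qualifier, "Participants who receive SCS for any reason and/or are indicated for sinonasal surgery will be considered non-responders for time points after SCS use" or surgery, which fits responder status at a visit and fits poorly with an event counted through Week 24. Protocol 9.3.2 uses nearly the same sentence for responder endpoints only. This shows what was probably intended. It does not remove the conflict, because the SAP paragraph names the two events and exempts neither from the coding sentence.

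One may also doubt that a dropout is ever missing on a yes/no check of medication taken. That is fair, but SAP 3.1.4.8 does not say so, and the default then applies.

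A baseline term has some support in Protocol 9.3.7. That section asks for region as well, and cannot supply a baseline where none exists. If leaving region out counts as otherwise noted, it still belongs in SAP 5.

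A reader might infer four stronger things that the documents do not support:

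- **That both events necessarily become the composite of SCS or surgery.** That is one of two literal readings, and SAP 3.1.4 contradicts both.
- **That none of the six models can be fitted.** 3CS, SNOT-22 and PGIS have baselines, so their models can be. For PGIC the responder rule is also sensible; only the covariate fails.
- **That the test could be picked after unblinding.** SAP 1 requires approval before the Week 24 lock and unblinding, and SAP 3.4.3 names logistic regression for the comparison. The fault is the p-value label.
- **That Kaplan-Meier is the required remedy.** Participants having rescue surgery leave the study (Protocol 3.7.13), so simple censoring would treat an informative competing event as ordinary dropout.

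**Conclusion.** The point holds as a conflict within the SAP and an undeclared departure from the protocol. Either literal coding of non-response contradicts the SAP's own derivation of the two event endpoints. Dropouts are handled differently for two closely related outcomes without a stated reason. Three of the six endpoints lack the required baseline value. Region has been dropped from the comparison, and the p-value carries the name of a different method's statistic.

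The distortion cannot be stated from the documents. Under assumed rates and the *yes* reading, a surgery odds ratio of 1.00 becomes 0.46 to 0.63, and a rescue-use odds ratio of 0.44 becomes 0.53 to 0.58. If the programmers follow SAP 3.1.4 alone, the coding distortion is nil.

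These are additional secondary endpoints outside the fixed testing sequence. The primary result, the key secondary tests and alpha are not affected.

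**What to change.** Amend SAP 3.4.3 and SAP 5 before the Week 24 database lock:

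1. Limit the non-responder rule and the missing-as-non-responder rule to the 3CS, SNOT-22, PGIS and PGIC responder endpoints.
2. Code surgery requirement and rescue medicine use only by their own event, as in SAP 3.1.4.8 and 3.1.4.9, with one stated dropout rule for both and no baseline term. If Kaplan-Meier is chosen for rescue medication, treat study exit for surgery as a competing event.
3. Name one test. Either CMH stratified by region and polyp status, as in the protocol; or logistic regression with treatment, region, polyp status and the endpoint's baseline where one exists (baseline PGIS for PGIC), with the treatment p-value taken from that same model.
4. List any departure from the protocol's CMH test in SAP 5.

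The cost is SAP wording. No new data, visits or sample size are needed.

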3.4.5 Subgroups

The primary and key secondary efficacy endpoints will be summarized descriptively for the ITT Analysis Set based on the following subgroup factors:

- Nasal polyp status (with nasal polyp vs without nasal polyp)
- Age (<65, ≥ 65)
- Gender (male, female)
- Baseline BMI categories (<25, ≥ 25 -<30 kg/m², ≥ 30 kg/m²)
- Race (Caucasian/White, Black/of African Descent, Others)
- Region (US vs EU)
- Ethnicity (Hispanic, non-Hispanic)

Formal subgroup analysis including the interaction by treatment group testing will be conducted in the ISE according to the prespecified ISE SAP.

Other subgroups may also be explored.

3.5 Pharmacokinetic Assessment

At Day 1 visit, the blood sample for plasma PK analysis will be collected before the LYR-210 administration/sham procedure. Subsequent blood samples (at Weeks 8, 16, 20, and 24) may be collected at any time of the day during the scheduled study visits. The concentration of MF in plasma will be measured at a central core lab.

A summary table will be used to present descriptive statistics (number, mean, SD, coefficient of variation, median, minimum, and maximum) of these PK parameters for the LYR-210 treatment group. Detail of the PK analysis (e.g., methods used in measuring the PK parameters, and how to handle below the limit of quantitation concentrations) will be documented separately.

3.6 Safety Analysis

Safety data will be summarized on the Safety Analysis Set.

3.6.1 Adverse Events (AEs)

An AE is any untoward medical occurrence (signs, symptoms, abnormal laboratory findings) in a participant regardless of relationship to the investigational product or procedure. Adverse events that occur prior to the insertion of the study treatment in the extension period will be included in this period summary.

All AEs will be coded to primary system organ class and preferred term using MedDRA version 24.1 (or later version).

Treatment emergent adverse events (TEAEs) are defined as AEs that start during or after the implantation procedure of study drug or sham procedure but no later than 31 days (>31 days) after discontinuation of study treatment.

An overview of AEs will be provided including counts and percentages of subjects (and event counts) with the following:

- Any TEAEs (overall and by maximum severity)
- Any study product related TEAEs (overall and by maximum severity)
- Any study procedure related TEAEs (overall and by maximum severity)
- Any serious AEs (SAEs)
- Any treatment-emergent serious AEs (TESAEs)
- Any TEAEs leading to discontinuation of study product
- Any TEAEs leading to discontinuation of study procedure
- Any AEs leading to death
- Any TEAEs related to COVID-19

Counts and percentages of subjects (and event counts) will also be presented by primary system organ class and preferred term for each of the categories in the overview. Listings will be presented specifically for SAEs and TEAEs leading to discontinuation of study product.

Adverse events of Special Interests (AESI) and TEAEs leading to Discontinuation

Certain treatment emergent adverse events will be designated as AESI. These categories are:

- Ocular safety adverse events
 - Cataract: Preferred Terms of Cataract, cataract cortical, cataract subcapsular, cataract nuclear

- Increase in IOP: Preferred Terms of Intra ocular pressure increased, Ocular hypertension
- Glaucoma: Preferred Terms of Glaucoma, Open angle glaucoma, Angle closure glaucoma
- Nasal mucosal safety adverse events
 - Mucosal injury: Preferred Terms of Nasal mucosal disorder, Nasal mucosal erosion, Nasal septum ulceration, Nasal septum perforation, Nasal mucosal erythema, Nasal mucosal ulceration
 - Epistaxis: Preferred Term of Epistaxis.

The number and percentage of participants reporting each category of AESI will be summarized by each treatment group. Difference and odds ratio in proportion of participants between the treatment groups will be calculated with its 95% confidence intervals.

Additionally, the difference and odds ratio in proportion of participants between the treatment groups and its 95% CI for the percentage of subjects with TEAEs leading to discontinuation of study treatment will be calculated.

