2.2.5 Safety endpoints

Safety endpoints include:

- 1. Treatment-emergent adverse events (TEAEs) and treatment-emergent serious adverse events (TESAEs) through Week 24.
- 2. Abnormal (clinically significant) laboratory values (hematology and chemistry) through Week 24.
- 3. Newly identified adverse endoscopic findings in middle meatus including epistaxis, mucosal erosion or ulceration, and perforation through Week 24.
- 4. Clinically significant increase of IOP through Week 24.
- 5. Newly identified or worsened cataract in one or both eyes by slit-lamp examination through Week 24.

For safety analysis incorporating the safety extension phase, the above safety endpoints will be summarized from Day 1 through Week 48 for the LYR-210 to LYR-210 and LYR-210 to Sham treatment sequences and from Safety Extension Day 1 through Week 48 for the Sham to LYR-210 treatment sequence.

3. Investigational Plan

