7.1 Adverse events and treatment-emergent adverse events

An AE is any untoward medical occurrence (signs, symptoms, abnormal laboratory findings) in a participant regardless of relationship to the investigational product or procedure. Each AE is either expected or unexpected as described below. The site is required to report Aes that occur during the study. These events shall also be classified according to the suspected causality by the study investigator.

Throughout the course of the study, all efforts will be made to remain alert to possible Aes or untoward findings. If AEs occur, the first concern will be the safety and welfare of the participant. Appropriate medical intervention will be undertaken. Any AE observed by the investigator or reported by the participants, whether or not ascribed to the investigational procedure or product, will be recorded on the participant's AE case report form (CRF). A new AE CRF will be used for each AE. All on-going AEs that result in early termination (ET) from the study or are deemed to be study product- or procedure-related by the site investigator will be followed until resolution or stabilization of the AE.

Documentation regarding the AE should be made as to the nature, date of onset, end date, severity, and relationship to study product, action(s) taken, seriousness, and outcome of any sign or symptom observed by the physician or reported by the participant upon indirect questioning.

A treatment emergent AE (TEAE) is an AE that occurs or worsens on or after initiation of the LYR-210 administration/sham procedure.

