7.6 Reporting adverse events

AEs are to be collected from the time a participant signs the informed consent form (ICF) until the completion of all follow-up visits. At each office or telephone/virtual visit during the study, AEs that have occurred since the previous office visit must be recorded. All participants will be evaluated for AEs or complications associated with the study procedure or the investigational product. The investigator will determine the severity and relationship of each event, as defined above. AEs observed during this study, regardless of severity or relationship to the study procedure or investigational product, will be recorded on the appropriate CRF.

Documentation of all new AEs or changes in previously reported AEs will be recorded. Preexisting diseases or conditions will not be reported as AEs unless there has been a substantial increase in severity or frequency of the problem, which cannot be attributed to the expected progression of the disease or condition.

The investigator will review the results of all clinical and laboratory tests as they become available. For each laboratory test result, the investigator will ascertain whether the result represents an abnormal (ie, clinically significant) CFBL for that individual participant. If this laboratory test result is determined to be a clinically significant abnormal CFBL for that participant, the value will be considered to constitute an AE.

All AEs will be coded using Medical Dictionary for Regulatory Activities (MedDRA) throughout the study.

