3.1.8.2 Algorithm for Treatment Emergent Adverse Events (TEAE)

TEAE is defined in Section 3.6.1.

For deriving the TEAE flag the following process of temporary date imputation is done for adverse event (AE) start date. The date imputation algorithm for incomplete adverse event start dates is described in Table . Classification of adverse event (TEAE or not) is then done using the imputed date.

In the following table, all dates are presented using an YYYY-MM-DD format. As an example, suppose First IMP administration = 2022-08-11 and several AEs have incomplete start dates.

Table 4. Imputation Rules for Missing AE start Date

Description of incomplete date	Imputed numeric date	Example	
		Character date	Imputed date
Day is missing			
YYYY-MM < YYYY-MM of [First IMP admin.]	YYYY-MM-01	2022-07-XX	2022-07-01
YYYY-MM = YYYY-MM of [First IMP admin.]	Min ([First IMP admin.], AE end date)	2022-08-XX	Min (2022-08-11, AE end date)
YYYY-MM > YYYY-MM of [First IMP admin.]	YYYY-MM-01	2022-09-XX	2022-09-01
Day and month are missing			
YYYY < YYYY OF [First IMP admin.]	YYYY-01-01	2021-XX-XX	2021-01-01
YYYY = YYYY OF [First IMP admin.]	Min ([First IMP admin.], AE end date)	2022-XX-XX	Min (2022-08-11, AE end date)
YYYY > YYYY OF [First IMP admin.]	YYYY-01-01	2023-XX-XX	2023-01-01
Day, month, and year are missing			

XXXX-XX-XX	Min ([First IMP admin.], AE end date)		Min (2022-08-11, AE end date)
------------	---------------------------------------	--	-------------------------------

YYYY = non-missing year, MM = non-missing month, DD = non-missing day, XX = missing field.

Actual data values as they appear in the original eCRFs will be presented in the data listings.

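### The SAP defines TEAEs by start date and adds a 31-day limit, while the protocol also counts worsening; the SAP declares no change

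*SAP*

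**What the plan says.** Protocol 7.1 gives the definition: "A treatment emergent AE (TEAE) is an AE that occurs or worsens on or after initiation of the LYR-210 administration/sham procedure". It sets no closing date. The period comes from the endpoint in Protocol 2.2.5: "Treatment-emergent adverse events (TEAEs) and treatment-emergent serious adverse events (TESAEs) through Week 24".

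SAP 3.6.1 says that TEAEs "are defined as AEs that start during or after the implantation procedure of study drug or sham procedure but no later than 31 days". The full limit reads "but no later than 31 days (>31 days) after discontinuation of study treatment"; the parenthesis contradicts the words before it, and the same phrase stands in SAP 3.3.8. The SAP does not say which date counts as discontinuation.

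SAP 3.1.8.2 describes the flag: "For deriving the TEAE flag the following process of temporary date imputation is done for adverse event (AE) start date", and then "Classification of adverse event (TEAE or not) is then done using the imputed date". It has no step for worsening and none for the 31-day limit.

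SAP 5 states: "There is no change from the protocol-specified statistical analyses". The Appendix C entry for 3.6.1 mentions only the AESI definition and its summary measures.

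**The concern.** TEAEs and TESAEs are the first safety endpoint in both documents. The definition decides which events enter the tables, so a narrower definition changes the analysis even if every table shell stays the same. A reader of the SAP is told that nothing has changed.

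The practical risk is in AEs that begin after consent but before the procedure. Protocol 7.6 collects AEs from consent, and the run-in lasts 2 to 4 weeks, extendable to day 35 (Protocol 3.5.2). If such an AE worsens or becomes serious after the procedure, the protocol counts it and the SAP as written may not. The AESI categories are subsets of the TEAEs. They and the TEAEs leading to discontinuation get between-arm differences and odds ratios with 95% confidence intervals, so they inherit the same gap.

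**Working it through.** The documents state no figure for this point, so there is nothing to reproduce. The check compares the texts and then counts days.

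**1. The two definitions**

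| Element | Protocol 7.1 | SAP 3.6.1 and 3.1.8.2 |
|---|---|---|
| Window opens | at initiation of the procedure | during or after the procedure |
| Qualifying event | new AE, or worsening of an existing one | AE whose start date is in the window |
| Window closes | not in the definition; endpoint runs through Week 24 | 31 days after treatment discontinuation |

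The opening is in effect the same. The other two rows differ.

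**2. Worsening.** Protocol 7.6 has sites record both new AEs and updates to AEs already reported. Neither document says that worsening opens a new record with a new start date.
- New record opened: the start date is after the procedure, and both definitions count it.
- Existing record updated: the start date stays before the procedure. The protocol counts it and the SAP does not.

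Among the AESIs this concerns mainly epistaxis and mucosal erythema or disorder. Erosion, ulceration, septal perforation, glaucoma and ocular hypertension are excluded at entry, whereas the epistaxis criterion bars only more than one qualifying episode before Screening.

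**3. The 31-day limit.** Assumption: discontinuation means matrix (or sham) removal on day R, in line with SAP 3.3.9, which counts exposure up to removal or dislodgement. The window closes on R + 31. The end-of-treatment-phase (EOTP) visit is due from R + 25 to R + 31, after scheduled removal and after any early termination (ET) visit, dual dislodgement included (Protocol 3.5.7, 3.5.8, Table 4).

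| Removal day R | Window closes, R + 31 | EOTP visit due | Days lost up to that visit |
|---|---|---|---|
| 138 | 169 | 163 to 169 | 0 |
| 141 | 172 | 166 to 172 | 0 |
| 144 | 175 | 169 to 175 | 0 |
| 57 (ET) | 88 | 82 to 88 | 0 |
| 85 (ET) | 116 | 110 to 116 | 0 |
| 113 (ET) | 144 | 138 to 144 | 0 |

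**4. Longer follow-up.** Protocol 7.8 has a participant who becomes pregnant in the treatment phase undergo removal, stay in follow-up through Week 24 and not enter the extension. If Week 24 here means Day 169 (the SAP target day), the uncounted days are 169 − (R + 31):
- R = 57: 169 − 88 = 81
- R = 85: 169 − 116 = 53
- R = 113: 169 − 144 = 25

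If removal is instead treated as an ET visit and follow-up ends at the EOTP visit, the gap is 0.

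**5. Fit within the SAP.** SAP 3.1 puts all AE data before extension insertion into the Week 24 analysis, and SAP 3.6.1 says the same for its period summary. With the 31-day limit, an AE could be in that data set yet missing from every TEAE table.

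**6. Weight of one participant.** With the planned 120 and 60 (SAP 2.2.4): 1/120 = 0.83 percentage points for LYR-210 and 1/60 = 1.67 for sham.

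**The case against.** The best defence is that little is lost in practice. Protocol 7.6 makes a pre-existing condition an AE once it has clearly become more severe or more frequent, and its onset can then fall after the procedure. Serious events still appear in the SAE row, which does not use the TEAE flag. Worsened endoscopic findings are tabulated separately (SAP 3.6.3). The protocol plans no formal safety tests. All of this stands and narrows the point. What remains is an AE that began between consent and Day 1 and was updated on the same record. Whether it counts depends on data-entry conventions that the documents do not give, and the SAE row does not replace the TESAE endpoint.

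Stronger readings of the 31-day limit are tempting, but the documents do not support them:
- *Early termination and dual dislodgement lose events, mostly in the LYR-210 arm.* The EOTP visit is due within the same 31 days in these cases, so the limit alone loses nothing up to that visit.
- *AEs between the limit and extension insertion are TEAEs in neither period.* Protocol 2.2.5 summarizes safety for participants who started on LYR-210 from Day 1 through Week 48, and the 52-week rules are in a separate SAP (SAP 4.2).
- *AEs should be counted to Day 210.* The windows that reach Day 210 in SAP 3.1.2.2 are for laboratory, ocular and endoscopy assessments. Counting AEs that far would overrun an endpoint defined through Week 24.

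**Conclusion.** The mismatch is certain from the text: the SAP drops worsening, adds a 31-day limit with an undefined starting date, and declares no change. The loss of worsening is the main part. It can remove events from the TEAE, TESAE, discontinuation and AESI summaries, provided that sites record worsening on the existing record.

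The 31-day limit is secondary. It costs nothing with an EOTP visit on time. Before Day 169 it can drop AEs only in participants followed beyond 31 days after removal; the pregnancy figures of 81, 53 and 25 days rest on reading Week 24 as Day 169. It cannot remove an AE that itself led to discontinuation.

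A reader might infer a bias between the arms. That is not shown: both rules apply to both arms, and the documents give neither the number of participants affected nor a direction. This should be corrected before the Week 24 lock, but it does not bear on the efficacy analysis.

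**What to change.** - In SAP 3.6.1, use the Protocol 7.1 definition, worsening included.
- In SAP 3.1.8.2, add a flag rule for an AE that began before the procedure and worsened afterwards, naming the date used for the worsening.
- For the Week 24 analysis, count in both arms up to extension insertion or, for participants who do not enter the extension, through the Week 24 endpoint period. State the day on which that period ends.
- Keep a 31-day window only as a secondary on-treatment table with a defined treatment end date. If the narrower definition is intended as the main one, declare it in SAP 5 with a reason.
- Check the parenthesis after the 31-day limit in SAP 3.6.1 and 3.3.8 against the original PDF, and correct it if it is really there.

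The cost is SAP wording and one programming flag before the Week 24 lock. No new data are needed, provided that the recorded AE updates carry a date.
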